with an amphotericin, persistent visual disturbances with voriconazole, allergic reaction with any compound, or other recognized drug-related AE) AND alternative licensed agents are either predicted to be ineffective or are contraindicated,

- d) **Inability to manage DDIs.** Inability to continue current therapy due to DDIs that cannot be managed AND alternative licensed agents are either predicted to be ineffective or are contraindicated,
- e) **Inability to produce therapeutic drug levels.** Inability to produce or maintain therapeutic blood levels with current therapy AND alternative licensed agents are either predicted to be ineffective or are contraindicated
- f) **An IV-only option (e.g., an amphotericin) has produced a clinical response AND it is standard practice to switch to an oral azole for completion of therapy AND** at least one of the following is true:
 - i) Azole-resistance is known based on susceptibility testing of the infecting isolate,
 - ii) Azole-resistance is predicted by PCR or similar molecular diagnostic tool,
 - iii) Azole-resistance is suspected based on epidemiological or clinical grounds (e.g., development of aspergillosis while on mould-active azole prophylaxis; history of lack of response to a mould-active azole at an early point in the therapeutic course),
 - iv) An azole would be acceptable therapy but it is known or predicted that unmanageable DDIs will occur
- g) **Other MM agreed inclusion.** Patient does not meet any of criteria a) to f), but treatment with F901318 is judged appropriate by the Investigator. Inclusion of patients based on this category must be agreed with the MM and the rationale must be documented.

4.3.1.1 *Inclusion Criteria for Extended Treatment Phase*

1. Patient has completed 84 to 90 days of treatment with F901318 in the main study phase.
2. In the Investigator's opinion the patient has potential to continue to benefit from extended treatment with F901318. The Investigator must discuss ET with the MM, and the MM must approve ET for each patient.
3. No other alternative treatment option is available.
4. Patient is willing to give informed consent for ET.
5. Patient is willing and able to comply with monthly visits to the clinic for assessments.

4.3.2 **Exclusion Criteria for Main Study Phase**

Patients will not be entered in the study for any of the following reasons:

1. Women who are pregnant or breastfeeding.

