6.3.2 Survival

All-cause mortality has been used historically as an endpoint in other similar clinical studies in IFD. All-cause mortality will be assessed using survival status and, if applicable, death details will be recorded in the eCRF. If the patient has died, the date and cause of death will be recorded, in addition to details required for SAE reporting (see Section 6.4.1.2).

Survival status will be recorded at Day 42, main study phase EOT, Day 84 and at the 4-week FU and included in the CSR. Information on survival status on Days 42 and 84 will be collected in all

patients, irrespective of when treatment was discontinued (*note that for patients planning to receive ET beyond Day 90, the Day 84 visit and the main study phase EOT visit will be combined into a single Day 84/EOS/EOT visit on approximately Day 90*).

Survival status will also be recorded at each ET visit and at the post-ET FU visit, and will be presented in the report addendum.

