Based on the DRC-adjudicated and Investigator-assessed mycological response categorized as Success/Failure, a response rate will be calculated based on all patients included in the mITT population with a baseline culture result available. Patients with a mycology evaluation of “No mycological Follow-up results available” will be assigned an outcome of presumed eradication if they are deemed a clinical success and a presumed failure if they are deemed a clinical failure, or clinical response is missing. Mycological success will include patients classified as a success or a presumed eradication. In addition a 95% CI for a single binomial proportion will be calculated.

All-cause mortality at Day 42, main study phase EOT, Day 84 and 4-week FU*

Mortality rates will be derived at Day 42, main study phase EOT, Day 84 and 4-week FU* based on all patients in the mITT population. In addition a 95% CI for a single binomial proportion will be calculated. Also, Kaplan-Meier analyses will be performed at Day 42, main study phase EOT, Day 84 and 4-week FU*, summarising median time to death (stratified by DRC-adjudicated disease category). A reported death will be carried forward for all future visits. A patient without reported death for the specific visit analysed (Day 42, main study phase EOT, Day 84 or 4-week FU*) will be censored for the specific visit analysed.

**Note: For patients planning to receive ET beyond Day 90, the Day 84 visit and the main study phase EOT visit will be combined into a single Day 84/EOS/EOT visit on approximately Day 90 and there will be no 4-week FU visit in the main study phase. As judged relevant, subanalyses will be performed to account for this difference in observation periods.*

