APPENDIX 4: PROTOCOL AMENDMENT HISTORY

The Protocol Amendment Summary of Changes Table for the current amendment is located directly before the Table of Contents (TOC).

Document History

Document	Date	Substantial	Region
Amendment 06	28 February 2020	Yes	Global
Amendment 05	30 October 2019	Yes	Global (not implemented)
Amendment 04	03 May 2019	Yes	Global
Amendment 03	28 November 2018	Yes	Global
Amendment 02	02 May 2018	Yes	Global
Amendment 01-01	07 March 2018	Yes	Local (Belgium)
Amendment 01	24 January 2018	Yes	Global
Original Protocol	19 December 2017	-	-

Amendment 05 30 October 2019

Amendment 05 was not implemented. Changes introduced to Amendment 05 which are relevant to Amendment 06 are included in the Summary of Changes for Amendment 06.

Amendment 04 03 May 2019

This amendment is considered to be substantial based on the criteria set forth in Article 10(a) of Directive 2001/20/EC of the European Parliament and the Council of the European Union.

Overall Rationale for Amendment 04

An extended treatment phase has been added to the study to allow continued treatment with F901318 for those patients who have benefitted from treatment with F901318 during the 90 day study treatment period, have no suitable alternative treatment options and would continue to benefit from extended treatment. In prior versions of this protocol, extended treatment has been provided via a Named Patient mechanism in each territory. As is standard with Named Patient mechanisms, the ability of the Sponsor to closely follow and support patients is limited and the data from patients utilizing this mechanism is not incorporated into study reports. As it has become clear that extended treatment is being found beneficial in approximately 25% of enrolled patients, Amendment 04 provides an explicit mechanism for this process that will allow the data from these patients to ultimately be provided as an addendum to the primary report for this study.

Extended treatment is to be requested by the Investigator and must be approved by the Medical Monitor. Patients will attend visits every 4 weeks during extended treatment to assess the safety

of continued treatment and to confirm by the evaluation of efficacy that continued treatment is justified. Assessment of the safety and efficacy of F901318 during extended treatment has been added as an exploratory objective. Detail has been presented of the assessments and procedures to be completed during extended treatment.

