Patient-reported outcomes have been added as an endpoint, to be collected by completion of the EQ-5D-5L questionnaire. This will provide additional insight into the benefits of treatment with F901318.

Further detail has been added for efficacy and safety assessments to clarify the processes for these assessments and to improve the consistency of reporting.

Description of Changes in Amendment 04:

Section Number and Name	Description of Change	Brief Rationale
Title page	
Sponsor address in the UK has been deleted.
 
The Project Manager details have been updated.
	
The Sponsor address is now in Austria.
 
The [REDACTED] Project Manager has changed.

Synopsis; Section 4.1	
The numbers of centres has been increased from 40 to 50.
	
The number of centres has been increased to facilitate enrolment of patients.

Synopsis; Section 3.2; Section 4.1; Section 6.3.4; Section 8.8.3	
Patient-reported outcomes have been added, to be collected by completion of the EQ-5D-5L questionnaire.
	
The EQ-5D-5L is a validated questionnaire to evaluate the effect of treatment on the patients quality of life, and will provide additional insight into the benefit profile of F901318.

Synopsis; Section 3.4	
An Extended Treatment Exploratory Objective has been added: To describe the efficacy and safety of prolonged treatment with F901318 for infections due to resistant fungi in patients lacking suitable alternative treatment options.
	
It is estimated that approximately 25% of patients who respond to treatment with F901318 may require treatment beyond the maximum of 90 days of treatment included in the main phase of this protocol. Safety and efficacy data collected from the end of the main study phase onwards will be evaluated as an exploratory objective.

Synopsis; Protocol body text throughout	
Reference to treatment with F901318 beyond Day 90 'via an extended dosing mechanism that is outside the scope of this protocol' has been replaced by a description of 'an extended treatment phase'.
	
This change provides a more structured approach to management of patients who have responded to treatment with F901318, and who have a clinical need and are likely to continue to benefit from extended treatment beyond Day 90 of the main study.

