- “Presumed Persistence” if they are deemed a clinical failure, or if the clinical response is missing at the specific visit.
- Patients with missing clinical response are assigned a response of “No mycological or clinical follow-up available”.

For statistical analysis of mycological response, values will be assigned to the DRC-adjudicated and Investigator-assessed mycological response as follows:

- Success (Eradication, Presumed Eradication),
- Failure (Persistence, Presumed Persistence, Recurrent/Emergent infections, death or any other response except Eradication or Presumed Eradication).

Patients withdrawn from study medication due to an unsuccessful overall outcome are required per protocol to return

Document: \\weedc-vnasc01\BIOSdata\F2G\F901318 [Redacted]
 Author: [Redacted] Version Number: 3.0
 Version Date: 06Apr2023
 Template No.: CS_TP_BS016 Revision 6 Reference: CS_WI_BS005
 Effective Date: 02Dec2019

F2G Ltd.
PROTOCOL F901318/0032

for the main study phase EOT visit but will not be asked to return for the Day 42 and/or Day 84 visits; these patients will be considered as failures at all subsequent timepoints.

For the 4-week follow-up visit, only patients who did not enrol in the extension treatment phase will be considered.

16.1.5.6. All-cause mortality rate at Day 42, main study phase EOT, Day 84, and 4-week follow-up

All-cause mortality rate at Day 42, main study phase EOT, Day 84, and 4-week follow-up is a secondary efficacy variable.

Survival status is captured on the Survival Status eCRF page.

Mortality rate at visit X is calculated as:

$$\frac{\text{Number of deaths up to and including visit X}}{\text{mITT population}}$$

For the 4-week follow-up visit, only patients who did not enrol in the extension treatment phase will be considered.

16.1.5.7. Patient-reported outcome at Day 42 and Day 84

[figure not shown]
A secondary efficacy variable is the quality of life (patient-reported outcome) [redacted] based on the EQ-5D-5L questionnaire. Patient-reported outcome is collected on the Health Questionnaire eCRF page.

The EQ-5D-5L health questionnaire is an assessment where the following five qualitative items are evaluated, i.e. does the patient have issues with:

- Mobility
- Personal care
- Usual activities
- Pain/Discomfort
- Anxiety/Depression

Document: \\weedc-vnasc01\BIOSdata\F2G\F901318 [redacted]
Author: [redacted] Version Number: 3.0
Version Date: 06Apr2023
Template No.: CS_TP_BS016 Revision 6 Reference: CS_WI_BS005

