16.1.6. MISSING DATA METHODS FOR SECONDARY EFFICACY VARIABLES

16.1.6.1. DRC-adjudicated and Investigator-assessed overall response, clinical response, radiological response, mycological response

- Patients with a missing overall response at a specific visit will be considered as failures at the visit.

Document:	\\weedc-vnasc01\BIOSdata\F2G\F901318\		
Author:		Version Number:	3.0
		Version Date:	06Apr2023
Template No.:	CS_TP_BS016 Revision 6	Reference:	CS_WI_BS005
Effective Date:	02Dec2019		

F2G Ltd.
PROTOCOL F901318/0032

- Patients with a missing clinical response at a specific visit will be considered as failures at the visit.
- In cases where the radiological test was not done, or results are not available, or the test is not applicable/relevant, this information will appear as such in outputs. In cases where the radiological response is missing (and not captured in one of the before mentioned options), it will be indicated as “Missing” in tables.
- Patients with a missing mycological response at a specific visit will be assessed according to criteria in [Table D](#) as either presumed eradication (success), presumed persistence or no mycological follow-up results available (failure) at the visit.

Note: All mITT patients will be counted in the denominator of the %/ rate calculation at every visit through Day 84, even if they discontinue early. For mycological response, all patients with mycological evidence at baseline will be counted in the denominator of the %/rate calculation.

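### Mortality at the 4-week follow-up leaves out every patient who enters extended treatment, all of them survivors to about Day 84, so it overstates mITT mortality at that visit unless those patients then die at a matching rate

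*SAP*

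**What the plan says.** SAP 16.1.5.6 gives the mortality rate at a visit as a fraction. The numerator is "Number of deaths up to and including visit X" and the printed denominator is the mITT population. One sentence then applies to the last of the four timepoints: "For the 4-week follow-up visit, only patients who did not enrol in the extension treatment phase will be considered". The same sentence accompanies the response endpoints in SAP 16.1.5.1 to 16.1.5.5.

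For the response rates, SAP 16.1.6.1 adds: "All mITT patients will be counted in the denominator of the %/ rate calculation at every visit through Day 84". The mortality subsection, SAP 16.1.6.2, has no equivalent note.

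Protocol 8.8.2 derives mortality at Day 42, end of treatment (EOT), Day 84 and the 4-week follow-up "based on all patients in the mITT population". An asterisk on the follow-up visit explains that ET patients have no such visit in the main phase, and that subanalyses will deal with the differing observation periods where judged relevant. SAP 3.3, which lists changes from the protocol, does not mention the restriction.

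The first ET entry criterion (Protocol 4.3.1.1) is: "Patient has completed 84 to 90 days of treatment with F901318 in the main study phase". On survival data, Protocol 6.3.2 says: "Survival status will also be recorded at each ET visit and at the post-ET FU visit", and assigns those data to the report addendum. ET visits are every 4 weeks, plus or minus 7 days (Protocol Table 3).

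**The concern.** The restriction selects on the outcome being measured. A patient must be alive at about Day 84 to enter ET, so the rule takes known survivors out of the calculation and no one who died earlier. The response endpoints have a reason for it, because the Data Review Committee does not assess ET visits (Protocol 6.3.3). That reason does not extend to survival, which is still recorded during ET.

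Describing all-cause mortality is a stated secondary objective. As written, the follow-up rate and its exact confidence interval belong to a subset defined after baseline, and nothing in SAP 16.1.5.6 requires the table to say so. A reader would take it for mITT mortality.

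**Working it through.** The documents give no expected mortality, event count or power for this endpoint, so there is no planned figure to reproduce. The check is direct arithmetic.

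**Inputs**
- N = 200, the planned enrolment (Protocol 4.1), taken as the mITT size for illustration.
- e, the share entering ET. The Amendment 04 rationale says "extended treatment is being found beneficial in approximately 25% of enrolled patients"; the change table for the same amendment says "approximately 25% of patients who respond to treatment with F901318 may require treatment". The first gives e of about 25%. The second gives about 10% if 40% respond (0.25 × 0.40; the 40% is an assumption). Both are used only to set a range.
- D = 50 deaths among non-ET patients by their own follow-up visit (assumed).
- m, mortality among ET patients in the 4 weeks after main-phase EOT (unknown, varied).

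**Formulas**
- Restricted rate: R = D / [N(1 - e)].
- All-mITT rate at the same point: A = (D + m·e·N) / N = (1 - e)R + e·m.
- Difference: R - A = e(R - m). R is too high for mITT whenever m is below R.
- With m = 0, R/A = 1/(1 - e): 1/0.90 = 1.11 and 1/0.75 = 1.33.

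**Results (Clopper-Pearson 95% CI, as in the SAP)**

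| Calculation | Rate | 95% CI |
|---|---|---|
| All mITT, m = 0: 50/200 | 25.0% | 19.2 to 31.6 |
| Restricted, e = 10%: 50/180 | 27.8% | 21.4 to 34.9 |
| Restricted, e = 25%: 50/150 | 33.3% | 25.9 to 41.5 |

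If 10% of the 50 ET patients (e = 25%) died in those 4 weeks, the all-mITT rate would be (50 + 5)/200 = 27.5%, still 5.8 points below 33.3%. For the two rates to agree, a third of the ET patients would have to die in 4 weeks.

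**If the denominator stays at mITT.** The printed formula could be read as keeping all 200 patients below the line while ignoring ET patients above it. The rate is then 50/200 = 25.0% whatever happens in ET, against 27.5% in the case just shown. The inflation disappears, but ET deaths are lost. The instruction to consider only non-ET patients fits the restricted denominator better, and the response-rate note stopping at Day 84 points the same way. The SAP does not settle it.

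**Direction against Day 84.** Follow-up is 4 weeks after the last dose and may fall before Day 42 or Day 84 (Protocol 5.1). Suppose a share s of the Day 84 deaths occur after the patient's own follow-up visit, with no other deaths added. The follow-up rate is then [D84(1 - s)] / [N(1 - e)], and it equals the Day 84 rate when s = e. With 50 deaths by Day 84 and e = 25%, s = 0 gives 50/150 = 33.3%, above the Day 84 rate of 25.0%. If 13 of the 50 deaths fall after the patient's own follow-up, the rate is 37/150 = 24.7%, slightly below it.

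**The case against.** A reader might infer that every death before Day 84 stays in the numerator, so that mortality must appear to jump after Day 84 even if nobody dies. The documents do not support this. Someone who stops drug on Day 20 has follow-up at about Day 48, and a death on Day 70 counts at Day 84 but not at follow-up. For the same reason, restoring ET patients does not turn the follow-up rate into a later point in the Day 42 and Day 84 series.

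A reader might also infer that the plan offers no mortality summary that can be followed over time. It does. SAP 16.1.7.5 plans Kaplan-Meier survival at Days 42, 84 and 112, and cumulative deaths at Days 42, 84 and 100 with no ET exclusion stated. This mitigation is partial. Patients are censored when last known alive on the main study, so ET patients leave the risk set at about Day 84 to 90, and the Day 112 estimate rests on non-ET patients after that.

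Nor is this a flat contradiction of Protocol 8.8.2, whose asterisk acknowledges the missing visit. But the protocol keeps all mITT patients as the base and offers subanalyses; the SAP makes the subset its only crude follow-up rate and does not declare the change.

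It is also fair that the protocol sends ET data to the addendum (Protocol 6.3.2 and 8.0), that this is one of four timepoints of a descriptive secondary endpoint, and that historical comparison is planned around Days 42 and 84 (Protocol 4.2). These points limit the consequence. They do not make the rate an mITT rate.

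**Conclusion.** The concern holds for the follow-up rate read as mITT mortality. The mechanism follows from the ET entry rule and needs no assumption. The direction depends on one condition: the rate is too high unless ET mortality in the 4 weeks after main-phase EOT reaches the cumulative non-ET mortality. The size is illustrative, at most a factor of about 1.11 to 1.33 for an ET share of 10% to 25% with no ET deaths in that window. It assumes that the restriction applies to both numerator and denominator. On the other reading the fault is uncounted ET deaths, so the denominator must be stated in either case. As a rate for patients not entering ET the figure is valid, but it is not labelled as such. No claim is made about whether it will lie above or below the Day 84 rate.

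**What to change.** In SAP 16.1.5.6:
- Delete the ET exclusion for mortality and state that the denominator at the 4-week follow-up is all mITT patients.
- Take ET patients' status 28 days after main-phase EOT from the first 4-weekly ET visit (not the start-of-ET visit, which may coincide with EOT) or from last known contact date, a source SAP 16.1.7.5 already allows.
- If a non-ET rate is also shown, label it 'patients not entering ET' and list it in SAP 3.3.

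In SAP 16.1.7.5, use the Day 112 Kaplan-Meier estimate for comparison over time, with ET survival dates included in place of censoring at the end of the main phase. Without that change, Day 112 does not solve the problem.

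The non-ET restriction can stay for the response endpoints.

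The cost is SAP wording and reprogramming of the follow-up mortality table and the Kaplan-Meier censoring rule; no new data are needed. The drawback is that a small amount of ET survival data enters main-phase output, so the protocol's split between study report and addendum (Protocol 6.3.2 and 8.0) needs a one-line exception.

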Effective Date: 02Dec2019

Answers to the five qualitative items include:

- None
- Slight
- Moderate
- Severe
- Extreme

The EQ-5D-5L health questionnaire also includes the quantitative item:

- Visual analogue scale (VAS) score, where the scale is numbered from 0 to 100. 100 means the best health the patient can imagine. 0 means the worst health the patient can imagine.

The EQ-5D-5L profile will be converted into a weighted health state utility value, the EQ-5D-5L Index, by applying a US-based value set derived from a standardized protocol developed by the EuroQol Group (Pickard et al). For derivation for EQ-5D-5L index score, please refer [Appendix 3 \(Reference⁴\)](#). The parameter estimate values are presented in [table 2](#). The parameter estimate for each questionnaire response is presented. i.e. Mobility Slight (MO2)= 0.096.

Please note that score for level 1 of each questionnaire item is 0. i.e. MO1=0, SC1=0, UA1=0, PD1=0 & AD1=0.

The overall health index score(HIS) for a patient at visit is derived by subtracting all the estimate values from 1, ie.HIS = 1 - (MO_i + SC_i + UA_i + PD_i + AD_i), where i=1,2,3,4,5 response score to respective questionnaire.

- If HIS=1 means perfect health.
 - HIS <1 means there is some negative impairment.

Please note that HIS cannot be >1.

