APPENDIX 3. EQ-5D-5L HIS CALCULATION

Table 2. Parameter estimates for main-effects models.

Dimension/level	Model 1: cTTO (Tobit with heteroscedasticity, censored at -1, RE) (preferred model)		
	Estimate	SE	P value
MO2	-0.096	0.015	<.0001
MO3	-0.122	0.016	<.0001
MO4	-0.237	0.018	<.0001
MO5	-0.322	0.016	<.0001
SC2	-0.089	0.014	<.0001
SC3	-0.107	0.017	<.0001
SC4	-0.220	0.018	<.0001
SC5	-0.261	0.016	<.0001
UA2	-0.068	0.015	<.0001
UA3	-0.101	0.016	<.0001
UA4	-0.255	0.013	<.0001
UA5	-0.255	0.013	<.0001
PD2	-0.060	0.013	<.0001
PD3	-0.098	0.017	<.0001
PD4	-0.318	0.015	<.0001
PD5	-0.414	0.017	<.0001
AD2	-0.057	0.014	<.0001
AD3	-0.123	0.018	<.0001
AD4	-0.299	0.016	<.0001
AD5	-0.321	0.015	<.0001

Document: \\weedc-vnasc01\BIOSdata\F2G\F901318\

Author:

Version Number:

3.0

Version Date:

06Apr2023

Template No.: CS_TP_BS016 Revision 6

Reference: CS_WI_BS005

Effective Date: 02Dec2019

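### SAP 16.1.5.7 subtracts the EQ-5D-5L estimates as positive decrements, but the Appendix 3 table that supplies them prints all 20 as negative

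*SAP*

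**What the plan says.** Two places in the SAP define the index.

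**SAP 16.1.5.7 (Patient-reported outcome)** gives the rule. The index "is derived by subtracting all the estimate values from 1", written in symbols as "HIS = 1 - (MO_i + SC_i + UA_i + PD_i + AD_i", with the sum closed after the anxiety/depression term. The values are to be taken from Table 2 in Appendix 3. The section illustrates one of them as "Mobility Slight (MO2)= 0.096", with no minus sign. On the reference level it adds "Please note that score for level 1 of each questionnaire item is 0". On direction and range it says "HIS <1 means there is some negative impairment" and "Please note that HIS cannot be >1".

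**SAP Appendix 3 (EQ-5D-5L HIS calculation)** holds Table 2, captioned "Parameter estimates for main-effects models". It lists levels 2 to 5 for each of the five dimensions, 20 estimates in all, and every one is negative: MO2 is -0.096, PD5 is -0.414, AD5 is -0.321.

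SAP 16.1.7.6 then calls for summary statistics of the index at each visit and of its change from baseline.

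**The concern.** The formula already carries a minus sign, and so does every coefficient in the table it draws on. Putting one into the other literally turns a deduction for ill health into an addition. Appendix 3 is the only place with the full coefficient set. Section 16.1.5.7 gives just MO2 and the zero scores for level 1, so the other 19 values must be read from the table whose sign conflicts.

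If the printed signs were used, the index would rise as health worsened and a deterioration from baseline would be reported as a gain of the same size. Evaluating patient-reported outcomes by EQ-5D-5L is a secondary objective (Protocol 3.2, SAP 2.2), so the result would appear in the study report.

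**Working it through.** **Inputs.** The estimates are from SAP Appendix 3, Table 2. Level 1 is 0 in every dimension (SAP 16.1.5.7). Magnitudes:

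| Level | MO | SC | UA | PD | AD | Sum D |
|---|---|---|---|---|---|---|
| 2 | 0.096 | 0.089 | 0.068 | 0.060 | 0.057 | 0.370 |
| 3 | 0.122 | 0.107 | 0.101 | 0.098 | 0.123 | 0.551 |
| 4 | 0.237 | 0.220 | 0.255 | 0.318 | 0.299 | 1.329 |
| 5 | 0.322 | 0.261 | 0.255 | 0.414 | 0.321 | 1.573 |

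Let D be the sum of the five magnitudes for a patient's profile.

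**Reading A: the sign shown in section 16.1.5.7 (MO2 = +0.096).** HIS = 1 - D.

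**Reading B: Appendix 3 values entered with their printed signs.** HIS = 1 - (-D) = 1 + D.

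| Profile | D | Reading A | Reading B |
|---|---|---|---|
| 11111 | 0 | 1.000 | 1.000 |
| 21111 | 0.096 | 0.904 | 1.096 |
| 22222 | 0.370 | 0.630 | 1.370 |
| 33333 | 0.551 | 0.449 | 1.551 |
| 44444 | 1.329 | -0.329 | 2.329 |
| 55555 | 1.573 | -0.573 | 2.573 |

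**Against the SAP's own statements.** The SAP says that 1 is perfect health, that values below 1 mean impairment, and that 1 is the maximum. Over all 5^5 = 3125 profiles:

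- Reading A runs from -0.573 to 1.000 and no profile exceeds 1. The stated bound and direction are reproduced.
- Reading B runs from 1.000 to 2.573. All profiles except 11111 exceed 1, that is 3124 of 3125. The stated bound and direction both fail.

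**Effect on change from baseline.** Since A = 1 - D and B = 1 + D, B = 2 - A for every profile. A change in B is therefore minus the change in A. For example, a patient who worsens from 22222 to 33333 changes by 0.449 - 0.630 = -0.181 under A and by 1.551 - 1.370 = +0.181 under B. The size is kept and the sign is reversed.

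**The case against.** The strongest reply is that section 16.1.5.7 is consistent within itself. The formula, the worked value of +0.096, the zero for level 1, the direction statement and the upper bound all agree under Reading A. Only the minus signs in Appendix 3 conflict. The magnitudes match in the one place where they can be compared (0.096 in both), and of the two readings only A satisfies the rest of the section. A competent programmer would probably see this. A literal-sign error would also be conspicuous, because every patient with any impairment would score above a stated maximum.

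All of that stands, and it rules out two stronger readings that a reader might infer. One is that following the SAP's formula reverses the scale. It does so only if the Appendix 3 signs are carried into the subtraction, which the worked value in section 16.1.5.7 speaks against. The other is that formula, table and bound all contradict one another. The formula and the bound agree, and the table alone conflicts with them.

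What the reply does not remove is that the rule and the table it cites cannot both be applied as printed, and that no sentence tells the programmer which sign governs. The bound is a note to the reader; the section does not say that it will be programmed as a check. A misreading of the PDF is an unlikely explanation, because the sign appears on all 20 rows.

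**Conclusion.** The point holds as a sign mismatch between SAP 16.1.5.7 and Appendix 3, Table 2. Read as section 16.1.5.7 evidently intends, the index is correctly directed, from -0.573 to 1.000. Read with the printed signs, 3124 of 3125 profiles exceed the stated maximum and every change from baseline reverses.

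The reach is small. Only the index and its change from baseline use these coefficients. The five items, their shifts and the visual analogue scale do not use them, and neither do the response and mortality endpoints. The index is summarised descriptively, with no test or decision attached. Protocol 8.8.3 plans the items and the visual analogue scale and does not name a utility index; the protocol synopsis mentions an overall score without defining it.

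A reader might infer that the reported index values are wrong. The documents give no basis for that, since they do not show which sign the program uses. The coefficients were taken as printed and were not compared with the published value set that the SAP cites; the sign mismatch does not depend on that comparison.

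**What to change.** Make one of two equivalent changes:

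- in SAP 16.1.5.7, write HIS = 1 + (sum of the signed Appendix 3 estimates), and show MO2 as -0.096; or
- keep the subtraction and print Appendix 3, Table 2 as positive decrements.

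In either case, add three check values: 11111 = 1.000, 21111 = 0.904 and 55555 = -0.573. Confirm that the index program reproduces them, and have it flag any value above 1.

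The cost is one line in the SAP and a brief check of the program. No data collection, sample size or other analysis changes.
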